The Verrata pressure guide wire (hereafter referred to as the "pressure guide wire") is a steerable guide wire with a pressure transducer mounted 3 cm proximal to the tip. The Verrata guide wire measures pressure when used with the SmartMap, ComboMap, s5 Series, and CORE Series of systems. The pressure guide wire has a diameter of 0.014" (0.36 mm) and is available in lengths of 185 cm or 300 cm* and also in straight or preshaped tips. The pressure guide wire is packaged attached to the connector with a torque device to facilitate navigation through the vasculature. It is possible that future iterations of the Verrata wire may be used in the study which will offer improved performance and reliability.

CONTRAINDICATIONS:

This pressure guide wire is not intended for use in crossing a total vessel occlusion.

Please review IFU attached.

Ethical Considerations

This protocol and any amendments will be submitted to a properly constituted Independent Ethics Committee (IEC) or Institutional Review Board (IRB), in agreement with local legal prescriptions, for formal approval of the study conduct. The decision of the IEC/IRB concerning the conduct of the study will be made in writing to the Investigator and a copy of this decision will be provided to the sponsor before commencement of this study.

Benefits

No direct benefits to the patient are expected. However, information gained during this study may lead to improved treatment workflows for patients with coronary artery disease in the future.

Risks

The Philips Volcano pressure guide wires used in this study are cleared for commercial use by the FDA and CE marked for commercial distribution in Europe for use in the coronary vessels as described in this protocol. Information related to contraindications, adverse effects, warnings, and precautions are included in the device Instructions for Use.

Risks associated with the use of pressure guide wires in patients with coronary artery disease are well understood, and incidence rates are very low. An extensive review of the safety of using pressure wires in 14 studies covering 1,284 patients revealed just 2 reports of arterial dissection (0.16%) and a single report of device entrapment (0.8%). The largest of these studies¹ (N=648) is that which reported the 2 dissections. Both were successfully managed and represented only 0.3% of the adverse events for this single study. A widely reported event was chest discomfort associated with the administration of adenosine in 86% of patients. Notably, the DEFINE PCI protocol will be using the instantaneous free-wave ration (iFR) which does not require the administration of adenosine.

¹ Ahmed N, Layland J, Carrick D, et al. Safety of guidewire-based measurement of fractional flow reserve and the index of microvascular resistance using intravenous adenosine in patients with acute or recent myocardial infarction. *International Journal of Cardiology*. 2016;202:305-310.

The single report of device entrapment occurred when a pressure guide wire was extended across a mechanical aortic valve² and was not used in the native coronary anatomy. The incidence of pressure guide wire entrapment or breakage in the Volcano complaints record is 0.0056% and 0.0048 (less than one chance in more than 17,000-20,000 uses), respectively.

Patients deciding to participate in this study are thus expected to bear standard risk associated with advancing and pulling back the pressure guide wire through the vasculature more times than would be typical in a standard PCI procedure. Site personnel are well-practiced in the use of pressure guide wires in the coronary anatomy, and are advised to use discretion in repeating a pressure reading in cases where this presents elevated patient risk due to any specific anatomical or physiological factor. Hence, the risk associated with the additional pressure wire procedures is considered standard.

Mitigation of Risks

The study site investigators will be selected for their experience and skill in Coronary interventions and familiarity with the use iFR and iFR pullback. Appropriate subjects will be selected using clearly defined inclusion/exclusion criteria to ensure that subject treatment is consistent with current medical standards and practices.

Risk – Benefit Analysis

. In terms of complexity, the Verrata Wire does not have moving or expandable parts, nor is any portion of the device implanted within the subject. Finally, the Verrata Wire is cleared by the FDA and CE marked for use in coronary arteries, and the device does not emit ionizing radiation. Patient participation is expected to provide insight for better managing ischemic coronary artery disease despite not experiencing any direct benefit. Hence, the overall benefits to the body of knowledge for treating coronary artery disease outweighs the risk associated with the additional pressure wire steps.

Data Handling and Record Keeping

² Marmagkiolis K, Cilingiroglu M. Radi pressurewire rupture and embolization to the right common carotid artery after crossing a Bjork-Shiley mechanical aortic valve. *Journal of Invasive Cardiology*. 2013;25(10):E191-E193.

Case Report Forms

This study will be performed using an electronic data capture (EDC) system. The Investigator and study site staff will receive training and support on the use of the EDC system. All eCRF data are to be completed by the Investigator, study coordinator, or other designated site personnel.

Source Documents

Investigators are required to maintain information in the study subject's medical records to corroborate data collected on the eCRF. Shadow charts are not appropriate or adequate for source documentation. Source data includes all information, original records of clinical findings, observations, or other activities in a clinical trial necessary for the reconstruction and evaluation of the trial. Source data are contained in source documents. Examples of source documents are: hospital medical records, clinical and office medical charts, laboratory notes, memoranda, subjects' diaries or evaluation checklists, pharmacy dispensing records, recorded data from automated instruments, copies or transcriptions certified after verification as being accurate and complete, microfiches, photographic negatives, microfilm or magnetic media, x-rays, print-outs of ECG, CDs/DVDs of angiograms and IVUS images, subject files, and records kept at the pharmacy, at the laboratories, and at medical-technical departments involved in the clinical study.

Data Queries

During the review of source documents and eCRF, any discrepancies will be queried by the monitor or its designee and must be resolved by the investigational site staff and Investigator in a timely manner. In addition, the monitor or its designee may also generate data queries during routine or remote review of the data. These queries will be sent to the site and must also be resolved in a timely manner by the Investigator and/or the study site staff.

Record Retention

All source documents (i.e., laboratory reports, progress notes, medical histories, physical and diagnostic findings, fluoroscopic and IVUS images and tracings, diagnoses and procedure dates, device disposition records, etc.) that support the CRFs of each subject must be retained in the files of the responsible Investigator for a minimum of two years following notification by Philips Volcano that all investigations of the device have been completed or discontinued.

If the responsible Investigator retires, relocates, or for other reasons withdraws from the responsibility of keeping the study records, custody must be transferred to

a person who will accept the responsibility. Philips Volcano must be notified in writing of the name and address of the new custodian.

Monitoring and Oversight

This study will be monitored according to the applicable requirements in the US Code of Federal Regulations (21 CFR Part 812, 50, 56), the guidelines in the International Conference on Harmonization (ICH) Guideline for Good Clinical Practice (GCP), the standards in the International Organization for Standardization (ISO) 14155:2011, and of the Declaration of Helsinki (2013).

Selection of Investigators

Study Investigators will be selected for their experience and skill in cardiovascular interventions and familiarity with the use of iFR physiology assessment. The Sponsor or designee may conduct a site visit to verify the qualifications of each Investigator, tour the site facilities, and evaluate the suitability of the site for participation in this study.

Individual Investigators will be evaluated by the Sponsor based on experience with the intended procedure, and ability to conduct the study according to the study protocol. Prior to enrolling subjects, each potential investigator must submit current, signed and dated curriculum vitae. Additional criteria may be applied to site and/or Investigator selection including:

- Adequate patient population to meet requirements of the study
- Adequate time to be personally involved in the conduct of the study
- Adequate research staff and resources to support the study
- Experience conducting clinical trials research
- Facility must be associated with an IRB/IEC that satisfies all applicable regulatory requirements, or be able to use a Central IRB/IEC that satisfies these requirements

Site Initiation Visits

Training of appropriate clinical site personnel will be the responsibility of the Sponsor. To ensure uniform data collection and protocol compliance, the Sponsor will review the

Protocol, techniques for identification of eligible subjects, instructions on data collection, and methods for scheduling follow-up visits in the defined follow-up window.

Interim Monitoring Visits

Routine monitoring visits will be made to ensure that the Investigator obligations are fulfilled and all applicable regulations and guidelines are being followed. These visits will ensure that the facilities are acceptable, the protocol is being followed, and the IRB has been notified of approved protocol changes as required, complete records are being maintained, appropriate and timely reports have been made to Philips Volcano and/or its designees and the IRB, and the Investigator is carrying out all agreed activities.

During monitoring visits, the monitor will perform, at a minimum, a review of source data for key variables for all enrolled subjects at each site (including but not limited to, inclusion/exclusion criteria, informed consents, endpoints, and safety) from the eCRFs compared against each subject's source documents. All available source documentation for monitored subjects will be reviewed for potential adverse device effects. Any discrepancies will be noted and resolved.

Study Close-out Visits

Upon completion of the study at a site, a close-out visit (remote or on-site) will be conducted. The monitor will ensure that the study related files at the investigational site are up to date and complete and that any outstanding issues from previous visits have been resolved. The monitor will ensure that the clinical trial materials and subject data are properly documented and stored for a minimum of two years following study completion. The Sponsor or designee will notify each site during the closeout visit of the current data storage requirements. Other topics that will be reviewed at this visit include: possibility of site audits, publication policy, notifying the IRB/EC of study closure, etc.

Direct Access to Source Data / Documents

The Investigator will permit study-related monitoring, audits, and inspections by the IEC/IRB, the Sponsor, government regulatory bodies, and compliance and quality assurance groups of all study-related documents (e.g., source documents, regulatory documents, data collection instruments, study data, etc.). The Investigator will ensure the capability for inspections of applicable study-related facilities (e.g., pharmacy, diagnostic laboratory, etc.).

Participation as an Investigator in this study implies acceptance of potential inspection by government regulatory authorities and applicable compliance and quality assurance offices.

Amendments to the Protocol

To alter the protocol, amendments must be written, receive approval from the appropriate Sponsor personnel, and receive IRB/IEC approval prior to implementation (if appropriate). All amendments will be distributed to all protocol recipients, with appropriate instructions.

Device Accountability

No device will be supplied to sites for this study.

Administrative Responsibilities

Independent Ethics Committee/ Institutional Review Board Information

The study will not be initiated before the protocol, informed consent, and any applicable subject information forms have been reviewed and received approval/favorable opinion from the local or regional Independent Ethics Committee/ Institutional Review Board. Should a protocol amendment be made that needs IEC/IRB approval and Authority notification/approval, the changes in the protocol will not be instituted until the amendment and revised informed consent (if appropriate) have been reviewed and have received approval/favorable opinion form the local IEC/IRB.

The constitution of the IEC/IRB must meet the requirements of the participating country/countries. A list of the IEC/IRB members must be provided. The Investigator (for EU: The Sponsor) must provide to the regulatory authorities, if applicable, the name and address of the IEC/IRB along with a statement from the IEC/IRB that is organized according to Good Clinical Practice and the applicable laws and regulations. The IRB/IEC must perform all duties outlined by the requirements of the participating country/countries.

Informed Consent and Subject Information

Prior to participation in the study, written informed consent must be obtained from each subject according to the regulatory and legal requirements of the participating site/country. Each signature must be dated by each signatory and the informed consent and any additional subject information forms retained by the Investigator as part of the trial records. A signed copy of the informed consent and any additional subject information must be given to each subject.

The subject must be informed that his/her personal trial-related data will be used by Philips Volcano in accordance with the local data protection law. The subject must be informed that his/her medical records may be examined by authorized sponsor personnel, quality assurance auditors appointed by Philips Volcano, by appropriate IEC/IRB members, and by inspectors from regulatory authorities.

Should a trial protocol amendment be necessary, the subject informed consent form may need to be revised to reflect the changes to the protocol. It is the responsibility of the Investigator to ensure that an amended consent form is reviewed and he has received

approval/favorable opinion from the IRB/IEC, and that it is signed by all subjects subsequently entered in the trial, and those currently in the trial affected by the amendment.

Investigator Responsibilities

Participating Investigators are required to accept the following responsibilities according to 21 CFR Part 812, and the ICH/ISO guidelines:

- Ensure that the investigation is conducted according to the Investigators agreement.
- Protect the rights, safety, and welfare of subjects.
- Obtain informed consent from each subject.
- Retain specific records and issue specific reports.
- Assure that an IEC/IRB is provided information for initial and continuing review of the study.
- Ensure that all work and services described within this protocol are conducted in accordance with the highest standards of medical practice and Good Clinical Practice.
- Ensure that all associated clinical and support staff members conduct the study in accordance with the protocol and amendments.
- Ensure that complete and accurate study data is collected and submitted to the sponsor.
- Ensure that the study regulatory binder, and study files containing CRFs, consent information, source documentation, records of adverse events and their resolution and all other relevant subject information are complete and up to date.

The Investigator is responsible for the conduct of the study at the site. Prior to enrollment of first patient, the Investigator must read and understand the Protocol and must sign and complete the Clinical Trial Agreement. The Clinical Trial Agreement requires agreement to all conditions of the Protocol and agreement to conduct the study according to all applicable regulations and guidelines.

Participation as an Investigator in this study implies acceptance of potential inspection by government regulatory authorities. The Investigator and/or designee must be available to respond to reasonable requests and queries made by authorized regulatory representatives during the audit process. The Investigator must provide the Sponsor or designee with copies of all correspondence that may affect the review of the current study or their qualification as an Investigator in clinical studies conducted by the Sponsor.

In the event the Investigator is contacted by a regulatory agency (such as the FDA) with regard to this study, the Investigator will notify the Sponsor immediately. The Investigator will ensure the capability for the inspection of applicable study-related facilities and records.

Discontinuation of the Trial by the Sponsor

Philips Volcano reserves the right to discontinue the trial at any time for any of the following reasons:

- Failure to meet expected enrollment goals,
- Any effectiveness/safety information that could significantly affect continuation of the trial or any other administrative reasons

Discontinuation of a Site by the Sponsor

Philips Volcano also reserves the option to terminate the participation of a study site at any time. Reasons for terminating the participation of a study site include, but are not limited to, the following:

- Subject enrollment is unsatisfactory
- Data recording is consistently inaccurate or incomplete
- Investigator does not adhere to the protocol or applicable regulatory guidelines in conducting the study
- IRB/IEC decides to terminate or suspend approval for the Investigator
- Study center or Investigator violates GCP or the study contract, disrupting the appropriate conduct of the trial
- Investigator asks to withdraw from study participation

Confidentiality

Information about study subjects will be kept confidential and managed according to the requirements of the local regulatory authority, as well as applicable US laws and regulations.

Personal Health Information (PHI) will be acquired during the consenting process of the subject and from the medical records. This information will be utilized to identify the subject and contact the subject for emergencies and follow up appointments. The PHI is part of the subject clinic chart, and will be secured in a locked office when not in use. To ensure that confidentiality is maintained, subject names will not be used in this evaluation in any other way. A unique identifying number will be used. This identification method will be consistent for each subject throughout the evaluation.

In the event that a subject revokes authorization to collect or use Protected Health Information (PHI), the Investigator, by regulation, retains the ability to use all information collected prior to the revocation of the authorization.

Publication Policy

The results of this study may be published or presented at scientific meetings. If this is foreseen, the Investigator agrees to submit all manuscripts, abstracts, or presentation materials to Volcano prior to submission. This allows the Sponsor to protect proprietary information and to provide comments based on information from other studies that may not yet be available to the Investigator. Any formal publication of the study with the input of Volcano personnel exceeding that of conventional monitoring will be considered as a joint publication by the Investigator and the appropriate Volcano personnel. Authorship will be determined by mutual agreement.

STATISTICAL ANALYSIS PLAN AND DETERMINATION OF SAMPLE SIZE

Target population

This analysis focuses on CAD Patients reporting an iFR < 90 in at least one coronary artery chosen from 25 US and International centers.

Data lock determination

The dataset will lock after all data needed for assessment of primary and secondary endpoints are reliably obtained, and any impossible data points are investigated and resolved.

Definition of Endpoints

This analysis classifies each patient into one of two categories: patients with residual ischemia (RI) and patients without. This data is distributed binomially, and the primary endpoint measures the proportion of patients with residual ischemia defined as iFR < 0.90 after successful PCI (p).

Primary Endpoint Analysis

The primary endpoint, the proportion of patients with RI defined as iFR < 90, is computed using maximum likelihood analysis. We compute the maximum likelihood estimate as $p = N^{-1} \sum_{s=1}^N y_s$, and Clopper – Pearson 95% confidence intervals.

The null hypothesis states no difference in the proportion of RI from 10%, or more formally, $H_0: p - 0.10 = 0$. The alternative hypothesis concludes any difference in RI from 10%, or $H_a: p - 0.10 \neq 0$.

Sample size computation

We assume a 10% rate of RI in the study (?) population which is defined as a residual stenosis of $\geq 50\%$ on QCA.

With 500 enrolled patients, type I error held at 5%, and the ability to detect a proportion of 15% RI, this study is powered at 90%.

Secondary Endpoint analysis

Kaplan Meier's product limit estimate computed as $S(t) = \prod_{t_j < t} \left(1 - \frac{d_j}{n_j}\right)$, where we partition time into j intervals t_j based on events, will measure time to event endpoints (listed as secondary endpoints 1-5). We conclude a significant survival difference between any two groups with the logrank test, and hold the expected type I error to 5%. We correct the type I error of the 5 related survival hypothesis using Benjamini and Hochberg's False Discovery Rate.

This protocol models Quality of life (secondary endpoint 6) as a mixed linear model,

$Q_{ijt} \sim N(\beta_0 + F_j[\beta_1 + b_{1j}T_j] + \beta_2T_j, \Sigma)$, where β 's describe fixed effects, b 's describe random effects, Σ describes a compound symmetric covariance matrix, and N the multivariate Gaussian distribution. We parameterize the covariance matrix with Compound symmetry, as opposed to autoregressive, because within time points will dominate variability compared to across time points.

The Kappa statistic will measure agreement between iFR and QCA's ability to detect RI by computing $\kappa = \frac{(p_e - p_1)}{(1 - p_1)}$, or the difference between empirical agreement and chance agreement divided by chance disagreement.

We estimate the proportion of cases in which the iFR would become non-significant if a focal stenosis demonstrated by iFR pullback were treated with PCI (Secondary endpoint 8) by

$$p = \frac{\#(\text{Number of non - significant iFR pullbacks})}{\#(\text{Patients})}$$

And assess the significance using a Binomial test.

The cause for impaired iFR is summarized using proportions, and the χ^2 test assess the null hypothesis that each cause of impaired iFR occurs at the same rate.

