As this is a nonrandomized study, all patients will receive standard of care therapy. All patients will undergo iFR prior to PCI in order to provide physiologic assessment of each vessel. Following PCI, all patients will undergo blinded iFR pullback in order to determine the proportion of patients with impaired post-procedure physiology.

Study Population

Number of Subjects

This study will enroll approximately 500 subjects at approximately 25 centers globally. Enrollment is expected to last approximately 1 year.

Subject Enrollment and Length of Participation

Subjects are considered enrolled in this clinical study when the pre-interventional iFR measurement is abnormal ($iFR < 0.90$) and with the intention to perform a PCI of at least 1 coronary stenosis. The expected duration of enrollment is approximately 12 months across all sites with each individual subject's participation lasting for 12 months after enrollment.

In the event that a post PCI iFR pullback is unable to be performed, the patient will remain in the study and continue to be followed during the follow up period.

Inclusion Criteria

To be eligible for this trial, subjects must meet all of the following criteria:

-
1. Subject must be ≥ 18 years old
 2. Subjects presenting with stable angina, silent ischemia or non-ST-elevation ACS (unstable angina or biomarker positive)
 3. Single vessel CAD with at least 2 separate lesions (≥ 10 mm apart) of $\geq 40\%$ stenosis or a single long lesion of ≥ 20 mm **OR** multi-vessel CAD, defined as at least 2 vessels with $\geq 40\%$ stenosis
 4. Pre-PCI iFR performed in all vessels intended for PCI
 5. Pre-PCI iFR of < 0.90 of at least 1 stenosis
 6. Subjects are willing to comply with scheduled visits and tests and are able and willing to provide informed consent.

Exclusion Criteria

If subjects meet any of the following criteria, he or she may not be enrolled in the study:

1. Pregnant or planning to become pregnant for the duration of the study
2. Acute STEMI within the past 7 days
3. Cardiogenic shock (sustained (> 10 min) systolic blood pressure < 90 mmHg in absence of inotropic support or the presence of an intra-aortic balloon pump).
4. Inotropic or temporary pacing requirement
5. Sustained ventricular arrhythmias
6. Prior CABG
7. Known ejection fraction $\leq 30\%$
8. Chronic Total Occlusion (CTO) of study vessel
9. Known moderate to severe mitral or aortic disease
10. Any medical comorbidity resulting in life expectancy < 12 months.

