- Troponin or CK-MB: If performed as SOC, at least one biomarker level should be obtained post PCI at 4-8 hrs. Post procedure. CK-MB is preferred but Troponin I/T may be drawn if CK-MB not available. Subsequent biomarker levels are highly recommended if initial post PCI biomarker is elevated and should be followed per local standard of care.
- Complete metabolic panel (if performed as SOC)
- EKG
- Event Assessment

Follow Up Procedures

1 month follow up (day 30 +14 days), 6 month follow up (day 180 +30 days) and 12 month follow up (day 365 +30 days)

Follow up can be done via telephone conversation.

- Current Anti-anginal medications
- Event Assessment
- Seattle Angina Questionnaire

Note: Event Assessment will be conducted at every encounter (scheduled and unscheduled) with the subject to specifically collect possible endpoints for CEC adjudication. Specifically, the subject should be asked regarding any cardiac hospitalization, myocardial infarction, repeat coronary angiography, repeat PCI, or recurrent angina.

Discontinued Subjects

Subjects have the right to withdraw from this study at any time and for any reason. Data that is collected prior to the subject's withdrawal from the study will be analyzed. The Principal Investigator has the right to discontinue a subject's participation in the study in the event of an underlying illness, adverse event, or protocol violation. Philips Volcano has the right to discontinue the study at any time. A complete final evaluation at the time of the subject's discontinuation should be made. The cause for subject withdrawal will be recorded in the appropriate case

report form (CRF). Discontinued subjects will not be replaced; i.e., overall study enrollment will not exceed 500 subjects.

Adverse Event Reporting

For the purposes of this study, because the Verrata pressure guide wire is commercially available, adverse event reporting for this study will be limited to ADEs, SADEs, and UADEs (per the below definitions).

Definitions

Adverse Event (AE)

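### The investigator may end a subject's whole follow-up for illness, adverse event or protocol violation; no later contact is described, and the plan does not settle how such subjects are analysed

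*Combined protocol and SAP*

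**What the plan says.** Discontinued Subjects allows the investigator to remove a subject; this may be done "in the event of an underlying illness, adverse event, or protocol violation". This is a right, not a duty, and it covers the whole study; there is no status for a subject who stops study procedures but is still followed. On exit, "A complete final evaluation at the time of the subject's discontinuation should be made", and the cause is recorded. The section describes no later contact, record review or vital-status check. It adds that "Discontinued subjects will not be replaced".

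Treatment Arms: "As this is a nonrandomized study, all patients will receive standard of care therapy". After the index procedure, Follow Up Procedures schedules contacts at 1, 6 and 12 months, which may be by telephone.

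Subject Enrollment and Length of Participation: if the post-PCI pullback cannot be done, "the patient will remain in the study and continue to be followed during the follow up period".

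On analysis, three places bear on these subjects:
- Discontinued Subjects: "Data that is collected prior to the subject's withdrawal from the study will be analyzed".
- Handling Missing data: patients who lack a primary or secondary endpoint are removed list-wise.
- Secondary Endpoint analysis: Kaplan-Meier estimates, and "We conclude a significant survival difference between any two groups with the logrank test". No censoring rule is given.

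**The concern.** A discontinuation clause of this kind usually protects a patient from further study treatment. Here the study-specific act is the blinded iFR and pullback at the index procedure. After that, ending participation removes no study exposure; it only stops the collection of outcomes.

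The permitted grounds are plausibly related to those outcomes. The protocol defines an adverse event as any untoward medical occurrence, whether or not it is device-related, so worsening angina or a rehospitalisation qualifies. Such patients are likely to carry a higher risk for the rest of the year. Kaplan-Meier and log-rank methods assume that those who leave have the same later risk as those who stay.

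At stake are objective 4 and the third hypothesis, that post-PCI iFR predicts later events. If low iFR acts through symptoms and illness, exits for illness could remove more events from the low-iFR group and shrink the association that the study is looking for.

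**Working it through.** **1. The plan's own figure.** Inputs from the SAP and the study summary: N = 500, null 10%, alternative 15%, two-sided 5%, exact binomial test. With equal tails the test rejects at X ≤ 36 or X ≥ 65 (tail probabilities under the null 0.0186 and 0.0180). Power at 15% is 0.908, which agrees with the stated 90%. The endpoint is measured at the index procedure, so exits after it leave this figure as it is.

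**2. Which rule applies to a discontinued subject.** Take a subject discontinued at month 4 without an event. Under Discontinued Subjects, four months of data are used, which in a Kaplan-Meier analysis means censoring at month 4. Under Handling Missing data, the one-year endpoint is missing and the subject is deleted. The sentence on using earlier data speaks of withdrawal and does not address investigator discontinuation separately. The two rules give different risk sets and nothing chooses between them.

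**3. Effect on the overall rate if censored.** The documents give no event or discontinuation rates, so these are assumptions: a 10% one-year rate, a share d discontinued at mid-year, and h times the hazard afterwards.

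Lost events = 500 × d × 0.5 × 0.10 × h. Total events = 50 + 500 × d × 0.5 × 0.10 × (h − 1).

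- d = 5%, h = 3: 3.75 of 52.5 events lost (7%). True rate 52.5/500 = 10.5%; Kaplan-Meier gives about 10.0%.
- d = 10%, h = 5: 12.5 of 60 events lost (21%). True rate 12.0%; Kaplan-Meier gives about 10.0%.

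**4. Censoring and deletion compared.** Assume a true rate r = 20%, exit of c = 2% of event-free patients, and exit of a share q of would-be event patients shortly before the event. Deletion gives r(1 − q) / [r(1 − q) + (1 − r)(1 − c)]. The Kaplan-Meier values were simulated.

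| q | Kaplan-Meier | Deletion |
|---|---|---|
| 5% | 19.3% | 19.5% |
| 10% | 18.4% | 18.7% |
| 20% | 16.5% | 16.9% |

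Both are low. By the formula, deletion understates the rate only when q exceeds c, that is, when those who leave are at higher risk than those who stay.

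**5. Effect on the association.** Assume 100 low-iFR patients at 16% and 400 others at 8%. HR = ln(1 − p1)/ln(1 − p0); D = 100·p1 + 400·p0; power = Φ(√(D × 0.2 × 0.8) × ln HR − 1.96).

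| Events lost | p1 v p0 | D | HR | Power |
|---|---|---|---|---|
| none | 16% v 8% | 48 | 2.09 | 0.53 |
| 10% in both groups | 14.4% v 7.2% | 43.2 | 2.08 | 0.49 |
| 20% in both groups | 12.8% v 6.4% | 38.4 | 2.07 | 0.44 |
| 20% in low iFR only | 12.8% v 8% | 44.8 | 1.64 | 0.26 |

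A simulation on other assumptions (15% of patients with low iFR, 30% v 18%, 2% of event-free patients leaving) gives the same direction: power 0.66 with no event patients lost, 0.62 with 10% lost in both groups, 0.58 with 20% in both, and 0.44 with 20% v 10%. With equal true rates (20% in both groups), the rejection rate stays near 5%.

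**The case against.** The case for leaving the clause alone has several sound parts.

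- The clause permits exit and does not require it. A reader might infer that the patients closest to an event will leave. The documents do not show that; the grounds include underlying illness, which may be long-standing or non-cardiac.
- An endpoint present at exit can be recorded. A final evaluation is required, events are asked about at every encounter, and the events committee reviews MACE. Only events after exit are lost.
- A reader might infer that these subjects are certain to be censored as non-informative. No censoring rule is written, and the one explicit missing-endpoint rule is deletion.
- A reader might say that stopping participation never removes exposure. Enrolment occurs at the abnormal pre-PCI iFR, and the Risks section accepts that the study adds wire passes. Between enrolment and pullback there is something to stop.
- The rule that keeps a patient in follow-up after a failed pullback does not contradict the clause. It is a specific exception, and it protects against one procedural cause of loss.
- Investigators and follow-up staff are to be blinded to post-PCI iFR, so exits could differ by iFR only through symptoms or illness. The scenario with loss in the low-iFR group alone is therefore an extreme.

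All of this limits the size and certainty of the effect. It does not supply follow-up after exit, and it does not say how these subjects are analysed.

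**Conclusion.** The point holds as a gap that is cheap to close. Exit on these grounds is allowed, nothing is collected afterwards, and the plan's statements on analysis do not settle whether such subjects are censored or deleted. If those who leave are at higher risk, both treatments understate one-year event rates. The hazard ratio is pulled towards one if loss is greater among low-iFR patients; with equal proportional loss it barely moves and the cost is power.

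The size cannot be fixed from the documents. The fall in power from 0.53 to 0.44 (equal loss) or 0.26 (one-sided loss), and the shortfall of 0.5 to 2.0 percentage points in the overall rate, rest entirely on assumed event, exit and hazard figures. A reader might take the drop in HR from 2.09 to 1.64 as the expected effect; it is the one-sided extreme.

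The primary endpoint and its 90% power are unaffected, provided that list-wise deletion is applied endpoint by endpoint. The consequence is confined to the secondary one-year endpoints of a single-arm pilot.

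**What to change.** In Discontinued Subjects, replace the investigator's right to discontinue with text to this effect: after the index procedure, illness, adverse events and protocol deviations are recorded but do not end follow-up. Stopping further study wire measurements during the procedure does not end follow-up either, in line with the existing rule for a pullback that cannot be done. Subjects leave only on withdrawal of consent, death or loss to follow-up; all others complete the 30-day, 6-month and 12-month event assessment and Seattle Angina Questionnaire, by telephone if needed.

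In the SAP, for the time-to-event endpoints, replace list-wise deletion with censoring at last contact, so that Handling Missing data agrees with Discontinued Subjects. Report remaining early exits by reason and by post-PCI iFR group. The censoring rule only makes the analysis definite; it is the continued follow-up that reduces informative loss.

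The cost is a few sentences and contacts that are already scheduled. No clinical decision is altered. The downside is a few calls to ill patients, who can decline. Outcomes not collected cannot be recovered by analysis, so the change should be made before follow-up ends.
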